## PRÉCIS

### Overview and Objectives

Polypharmacy, defined as five or more medications, is common in older patients discharged to skilled nursing facilities (SNFs) and is associated with adverse health outcomes. As part of a recent VA project, we prospectively collected medication data for 134 hospitalized, older Veterans. These data showed that, on average, 14.2 medications were ordered for Veterans discharged to SNF, which included 2.5 medications newly prescribed in the hospital that met criteria for being potentially inappropriate medications (PIMs). Moreover, 75% of these Veterans had two or more geriatric syndromes. Geriatric syndromes are clinical conditions common in older adults such as cognitive impairment, unintentional weight loss and falls. The co-occurrence of multiple syndromes is associated with loss of independence and higher healthcare utilization. All Veterans with polypharmacy also had one or more medications associated with geriatric syndromes. The prevalence of polypharmacy and multiple geriatric syndromes may partially explain why these patients often have poor health outcomes after SNF discharge. Recent data suggests that only 28% of patients discharged from SNF are living at home 100 days later, and 35% experience an adverse drug event.

There is a dearth of evidence related to the management of multiple co-existing geriatric syndromes, and few interventions have been implemented to reduce medications while also monitoring health outcomes. The relationship between polypharmacy, adverse drug events and geriatric syndromes in the VA population supports the rationale for an intervention focused on deprescribing medications before hospital discharge. We have pilot-tested a multifaceted intervention (Drug Reduction in Older Patients, DROP) to engage patients and providers to reduce the number and/or dose of medications prior to hospital discharge. The proposed randomized, controlled trial is powered to evaluate the effect of this intervention on a reduction in medications as defined by the total number of prescribed medications, the number of PIMs, anticholinergic and sedative drug burden and the number of medications associated with geriatric syndromes. In addition, we will collect relevant data on the prevalence and severity of geriatric syndromes and other clinical outcomes. We also will use a hybrid research design to evaluate both effectiveness and implementation issues to better inform future adoption and sustainability. Our overarching hypothesis is that a hospital-based intervention to safely reduce the total number of medications represents the most feasible way to impact multiple health-related outcomes among older Veterans. Our Specific Aims reflect the primary outcomes that are the focus of the analyses, although we also will measure secondary outcomes related to VA healthcare utilization and patient safety:

**Specific Aim 1:** Implement a patient-centered deprescribing intervention (DROP) in the hospital to reduce the total number of medications Veterans are prescribed at hospital discharge.

**Hypothesis 1a:** DROP will result in a significant reduction in total medication exposure due to discontinuations and dose reductions at hospital discharge, SNF discharge and 90-days after SNF discharge.

**Hypothesis 1b:** DROP will result in a significant reduction in the number of potentially inappropriate medications (PIMs) at hospital discharge, SNF discharge and 90-days after SNF discharge.

**Hypothesis 1c:** DROP will result in a significant reduction in the anticholinergic and sedative drug burden at hospital discharge, SNF discharge and 90-days after SNF discharge.

**Hypothesis 1d:** DROP will result in significantly fewer medications associated with geriatric syndromes at hospital discharge, SNF discharge and 90-days after SNF discharge.

**Specific Aim 2:** Document the effects of a Veteran-centered deprescribing intervention (DROP) on medication adherence, health status, and geriatric syndromes.

**Hypothesis 2a:** DROP will result in a significant improvement in medication adherence and self-rated health status at 7 and 90 days after SNF discharge.

**Hypothesis 2b:** DROP will result in a lower prevalence and severity of geriatric syndromes at 7 and 90 days after SNF discharge.

**Specific Aim 3:** Evaluate intervention implementation to inform future adoption and sustainability.

**Aim 3a:** Identify patient-level barriers and facilitators of DROP.

[figure not shown]
**Aim 3b:** Identify VA and Non-VA provider-level barriers and facilitators of DROP.

**Aim 3c:** Identify system-level factors that influence sustainability after hospital discharge.

## Study Design and Outcomes

### Overview of Design

**Figure 1. Schematic of Study Design**

### Study Setting

The Nashville VA Medical Center is part of the Tennessee Valley Healthcare System (TVHS), which serves a diverse Veteran population in terms of income, geography and education level. We will target Veterans discharged from the Nashville VA hospital to any SNF, although the most common SNF locations include the TVHS York campus and 20 contract VA homes in surrounding areas.

### Interventions and Duration

The intervention occurs during the Veteran's hospital stay (Figure 1: Phase 2). This phase includes identification of medication for deprescribing, an interview to determine Veteran preference for deprescribing, and discussion with the Veteran's inpatient treatment team. The inpatient treatment team incorporates the agreed upon final deprescribing actions in the Veteran's hospital discharge orders. The intervention ends at the point of hospital discharge.

### Study Population and Sample Size

Eligible Veterans are age  $\geq 50$  with polypharmacy as defined by  $\geq 5$  medications based on the pre-hospital admission; ability to provide consent (or proxy); speaks English; does not reside in long-term care or receive hospice services; have a recommendation or referral to a skilled nursing facility (SNF). All eligible Veterans will be approached for consent with an original enrollment goal of 540.

The population and sample size were adjusted mid-study due to the significant enrollment and retention challenges caused by the COVID-19 pandemic. It was determined that a sample of 260 Veterans was sufficient to provide power greater than 93% for both the primary and secondary outcomes. Additionally, Veterans who were recommended SNF placement but ultimately discharged from hospital to home were approved to remain in study, which improved the study retention rate.

## BACKGROUND AND SIGNIFICANCE

### Background on Condition, Disease, and Primary Study Focus

Geriatric Syndromes represent clinical conditions that share underlying causative factors and involve multiple organ systems. The most commonly cited geriatric syndromes include: incontinence, depression, cognitive impairment, delirium, unintentional weight/appetite loss, mobility impairment, pressure ulcers and falls. However, no published studies include measures of all these conditions in one patient population. Multiple syndromes are common in older adults and predictive of poor health outcomes, even when controlling for age and illness severity. Approximately 50% of hospitalized patients aged 65 and older experience two or more syndromes, with one or more syndromes either developing or worsening during the acute care episode. Patients discharged from the hospital to SNF are at higher risk for loss of independence relative to patients discharged home, and our preliminary data showed that 47% of hospitalized Veterans discharged to SNF had two or more geriatric syndromes. Moreover, each Veteran was prescribed an average of 5.4 medications associated with one or more geriatric syndromes (*Preliminary Studies*). A separate study of community-dwelling Veterans aged 65 and older with polypharmacy, as defined by five or more medications, showed that 43% had one or more geriatric syndromes, and the strongest predictor of an adverse drug event was the number of medications added to their regimen during a 12-month timeframe. These data provide a strong rationale for our overarching hypothesis that reducing medications for older Veterans will favorably impact geriatric syndromes and other health-related outcomes, such as adverse drug events.

Polypharmacy is common among older patients. Among hospitalized patients, polypharmacy has been most commonly defined as five or more medications to as many as 10 or more, also described as, “hyper-polypharmacy”. About 45% of older hospitalized patients are discharged on five or more medications. Older patients have an increased prevalence of multi-morbidity; thus, it is not surprising polypharmacy is common. However, a substantial number of prescribed medications may be unnecessary. Studies have found that > 90% of inpatients are taking at least one inappropriate medication. Several studies have shown that up to 43% of medications taken by older patients lacked a clear indication, and 5%-11% of medications may be unintentionally prescribed for the same indication. Even when a clear indication exists, medications may be inappropriate when considering drug-drug or drug-disease interactions. These medications, also known as potentially inappropriate medications (PIMs), have been defined by multiple criteria such as the Beers list and the Screening Tool of Older Persons’ potentially inappropriate Prescriptions (STOPP) Beyond medical appropriateness, some medications may be costly or have inconvenient dosing that decreases adherence. Finally, prescribed medications may be inconsistent with a patient’s goals of care.

Although most studies have been conducted in non-VA hospital settings, two studies reveal similar rates of polypharmacy and prescribing problems among VA patients. Most recently, a large study involving 462,405 Veterans aged 65 and older examined prescribing quality using VA pharmacy data. Results showed that Veterans were prescribed a median of five medications, and 50% were identified as having one or more types of ‘prescribing problems’ as defined by the following categories: inappropriately high dose (12%), drug-drug interactions (30%), drug-disease interactions (3%), potentially inappropriate per the Beers list (26%) or other high-risk drugs (26%, e.g., warfarin, insulin, and/or digoxin). This study also showed that the total number of medications was the strongest predictor of each type of prescribing problem. Similarly, an earlier study with 196 community-dwelling Veterans aged 65 and older prescribed 5 or more medications showed that 65% were taking one or more medications deemed clinically inappropriate and 57% were taking at least one medication deemed ineffective, not indicated or duplicative. Most importantly, however, the frequency of inappropriate medications increased as the total number of medications increased from a mean of 0.4 per Veteran among those taking five to six medications, to 1.1/Veteran among those taking seven to nine medications, and 1.9/Veteran among those taking 10 or more medications (i.e., hyper-polypharmacy). Underuse also occurred but was much less common, especially for those taking more than eight medications.

These studies demonstrate the prevalence and potential inappropriateness of polypharmacy among older patients in (non)VA healthcare settings. Other studies have shown that polypharmacy can lead to multiple harmful outcomes among older community-dwelling and hospitalized populations. These outcomes include decreased medication adherence, increased adverse drug events, and increased health care utilization and costs. Polypharmacy and a variety of drug indices that quantify drug burden also have been associated with the development of geriatric syndromes including long-term cognitive impairment, delirium, falls, frailty, urinary incontinence, and weight loss. The number of syndromes related to polypharmacy supports our hypothesis that polypharmacy may be contributing to geriatric syndromes.

## Study Rationale

### Alignment with VA Priorities

The study will examine the quality of care for hospitalized Veterans as they transition from acute to post-acute care and, subsequently, to home. The focus of this study is on polypharmacy among a vulnerable group of older Veterans who typically experience frequent care transitions and high healthcare utilization. The intent of the Veteran-centered intervention is to deprescribe unnecessary and potentially inappropriate medications to improve adherence and health status, which aligns with VA HSR&D research priority B, topic #3: *assesses an intervention that encourages Veterans to be more actively engaged participants in their health care and decision-making by improving communication and interactions between providers and Veterans.*

### Interventions to Deprescribe Medications and Knowledge Gaps

In recognition of the potential harms of polypharmacy, numerous studies have evaluated efforts to improve medication prescribing for older patients. Most interventions have applied the use of explicit criteria to reduce inappropriate prescribing with tools such as the Beers or STOPP, while a few considered other patient-centered factors (e.g., cost, convenience, life expectancy). Trials commonly use pharmacists, physicians or interdisciplinary teams to implement deprescribing protocols. However, there are several important gaps in knowledge, which this proposal will address. First, few interventions have been initiated in the hospital setting, and no deprescribing interventions have targeted older patients transitioning from acute to post-acute care, which may be an opportune time to deprescribe. The few trials that have been conducted have been disease-focused on deprescribing specific types of medications. Second, few trials have incorporated patient preferences into the decision-making process. A recent VA study implemented an electronic health record algorithm to identify medications for deprescribing; however, patients were not explicitly involved in the decision process. A recent qualitative study that included community-dwelling Veterans aged 65 and older with polypharmacy (mean = 13 medications/Veteran) demonstrated that most Veterans expressed a desire to take fewer medications. Finally, although most of the trials reported improvements in medication appropriateness, *there has been no study to evaluate the effects of deprescribing on health outcomes.*

### Preliminary Data

Our interdisciplinary research team has performed innovative, critical preliminary work that supports the rationale and feasibility of the DROP trial. This work includes (1) a determination of the prevalence of multiple geriatric syndromes in Veteran hospitalized older patients discharged to SNF; (2) identification of the potential link between polypharmacy and specific medications with contributing side effects to geriatric syndromes; and (3) a pilot-tested patient-centered deprescribing intervention (DROP).

We examined geriatric syndrome and polypharmacy prevalence in a predominately male (96%), White (86%) Veteran sample (average age 74±10) discharged to SNF (N=134). Overall, 75% endorsed symptoms for two or more syndromes and 43% endorsed symptoms for three or more syndromes, with an average of 2.6 syndromes per Veteran. Polypharmacy was almost universal among both Veterans. Specifically, 99% of Veterans were prescribed ≥ 5 medications and 80% were prescribed ≥ 10, with a mean of 14.2 (± 5.3) per person at hospital discharge to SNF. Discharge medication lists included an average of 2.5 medications per patient that met criteria for being potentially inappropriate (PIMs), with 1.0 newly prescribed PIM during their hospital stay.

We implemented a structured patient-centered intervention protocol (DROP) to reduce the total number of medications prior to hospital discharge among a sample of non-Veterans. Our deprescribing protocol was based on a conceptual framework that considers patient and disease factors, goals of care, treatment targets and the duration of treatment required for benefit. This framework also considers the clinical context of the patient's care and providers' willingness to deprescribe (provider barriers and facilitators). Finally, **patient preferences were viewed as a key component that informs final deprescribing actions** by identifying medications the patient is willing to deprescribe (e.g., including facilitators such as poor compliance, side effects or cost burden) and potential barriers (e.g., concern about symptoms worsening). The results of two recent qualitative studies revealed that most Veterans with polypharmacy expressed a desire to take fewer medications and the importance of involving the patient in the decision process related to medication changes to improve adherence. In addition, a survey of VA providers showed that assistance with follow-up, which a SNF care setting provides, and increased patient involvement in prescribing decisions were rated as two of the most preferred interventions to improve provider ability to discontinue medications.

The DROP intervention was implemented for 20 hospitalized patients referred to SNF and a control group of 20 patients, who received routine hospital care. The intervention and control groups had a comparable number of total medications upon hospital enrollment. Overall, the research team identified an average of 12.75 ( $\pm$  6.08) medications/patient for potential deprescribing based on initial chart review. The patient preference interview (intervention patients only) resulted in an average of 10.2 ( $\pm$  4.5) *changes* (e.g., dose adjustments) to the initial recommendations based on chart review only. The large number of changes in recommendations demonstrates the importance of involving the patient in the decision process. Recommendations were communicated to the inpatient team and outpatient provider(s) for the intervention group only. The DROP pilot resulted in an average of 12.6 total deprescribed medications in the intervention group ( $P < .001$ ), which included 6.1 pre-hospital medications (Table 3. Total deprescribed). The control group had an average of 6.5 total (4 pre-hospital) deprescribed medications as part of routine hospital care.

The results of the DROP intervention demonstrate our ability to reduce the total number of medications, PIMs, and medications associated with geriatric syndromes through a patient-centered deprescribing protocol implemented during the hospital stay. Because our protocol included dose reductions, we were able to reduce the DBI from enrollment to hospital discharge. The intervention also demonstrates the importance of involving the patient in the decision-making process along with the inpatient team and outpatient providers. Our patient preference interview is a unique component of our intervention and one that is absent from most prior studies.

#### **Innovation:**

This trial is advancing science in multiple ways:

- 1) One of the first controlled intervention trials designed to improve post discharge outcomes for the high-risk population of older Veterans transitioning from hospital to SNF to home. Healthcare costs are increasing for this patient population, and they are at high risk for medication-associated complications and newly acquired geriatric syndromes.
- 2) Although the number of medications is strongly associated with increases in geriatric syndromes, it is unknown whether reducing medications will improve geriatric syndromes. This trial will generate data to evaluate the impact of medication reduction on Veteran health outcomes.
- 3) To date, there have been no controlled intervention trials focused on reducing the number of medications prescribed for hospitalized patients discharged to SNF, and the proposed intervention is one of the first to explicitly incorporate Veteran preferences into deprescribing efforts, which is consistent with Veteran-centered care initiatives. Moreover, our preliminary data show that incorporating patient preferences in the intervention protocol significantly changes these clinical decisions.
- 4) The proposed trial will evaluate both clinical effectiveness and implementation to inform the potential for DROP to be adopted into VA clinical practice.

## STUDY DESIGN

The study is a 3-year, randomized controlled clinical intervention trial at a singular VA medical center.

Primary Outcomes are change in total number (and/or dose) of medications including potentially inappropriate medications, number of medications associated with geriatric syndromes, and medications that contribute to anticholinergic and sedative drug burden.

Secondary Outcome is the impact of deprescribing on geriatric syndromes, medication adherence, and self-rated health status.

Implementation Science Outcomes are to identify patient and provider level barriers and facilitators as well as system-level factors required for sustainability.

Eligible Veteran population is aged 50 years or older, experiencing polypharmacy (based on pre-hospital medications), and hospitalized at Nashville VA Medical Center with a recommendation for skilled nursing facility care. Exclusion criteria include limited life expectancy (less than 6 months or hospice admission), non-English speaking, no telephone, admitted from long-term care facility, incarcerated, no valid surrogate (if unable to consent), or enrolled in another drug trial.

The timeline for the study is 3.5 years with enrollment beginning October 2019 with enrollment closing in November 2022. Final follow-up ends in March 2023.

The DROP intervention is a deprescribing protocol that considers patient and disease factors, life expectancy, goals of care, and appropriate treatment targets. Medication-specific factors such as drug-drug interactions, drug-disease interactions, and drug-specific safety profiles are also incorporated. Finally, Veteran preferences are key to final deprescribing actions by identifying the medications Veterans are willing to deprescribe. The inpatient (hospital) treatment team makes the final decision on deprescribing and incorporates the changes in the hospital discharge orders. In this intervention, deprescribing is defined as either stopping a medication or reducing the dose/frequency of a medication.

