## Primary Outcomes – Medications

Total number of medications: Data collection begins with the Veteran's Essential Medication Review List (EMLR). After this list is abstracted from the medical record, a study NP or PharmD pulled the Controlled Substance Monitoring Database report, called non-VA pharmacies for recently filled prescriptions, reviewed non-VA medical records (i.e., outside hospital or SNF records), and interviewed the Veteran or their surrogate. We included all medications, either prescription or over-the-counter (OTC) that were administered by the following routes: oral, intravenous, intramuscular, sublingual, or ophthalmologic. Veterans (or their surrogate) were given specific prompts if they reported no OTC usage, for example, asking them if they take anything for constipation or allergies. If a patient was admitted from an institutional setting (e.g., outside hospital, SNF, ALF), we request a copy of the medication administration record from the previous 30 days. Medications are considered current/active if the Veteran took it within 30 days of hospitalization. The hospital discharge and SNF discharge medication lists, serve as the outcome data for those respective time points. During the follow-up calls, the study NP or PharmD systematically asked the Veteran for the status of each medication on the enrollment list and discharge lists to determine if and how they are taking it. Afterwards the study clinician prompted the Veteran for any new medications they may be taking.

Potentially Inappropriate Medications (PIMs): We used previously published and validated lists including the Beers criteria, the STOPP criteria, and the RASP list, which have a large degree of overlap. The total number of PIMs is the sum of medications that are found on these lists.

Drug Burden Index (DBI): This score is calculated separately for anticholinergic and sedative medications, which have been linked to functional impairment, falls, and delirium. The DBI is the sum of each individual anticholinergic/sedative medication's prescribed daily dose divided by the sum of the minimum effective dose (per the FDA minimum recommended dose) and the patient's daily dose. The DBI is calculated for all medications including OTCs. We will calculate the DBI at each timepoint, and this will capture dose reductions even when the total number of medications is not reduced.

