### Outcomes

**Hypotheses 1a -1b:** Among participants assigned to the intervention group, we will summarize both the number of deprescribing *recommendations* and the number of actual medication *changes* at hospital and SNF discharge and 90-days following SNF discharge. The effect of the intervention on the total number of medications, PIMs, and medications associated with geriatric syndromes at hospital discharge, SNF discharge, and 90-days following SNF discharge will be assessed using mixed effects Poisson regression, allowing for overdispersion (more or less variability than is expected under the Poisson regression model), and adjusting for measurement time point (as a categorical covariate) and the total number of medications at enrollment and the interaction of intervention and time point. The heterogeneity in outcome measures across participants will be modeled using a random intercept term, indexed by subject. Heterogeneity among VA providers and SNFs in the effectiveness of intervention will be modeled using a random intervention effect, indexed by VA provider and SNF. The overall intervention effect will be evaluated using a Wald-type multiple degree-of-freedom test against the null hypothesis of no effect at any time point. The intervention effect at each time point will be summarized using a Wald-type 95% confidence interval. Model fit will be assessed by examining the associated Pearson residuals and other graphical methods. Alternative regression techniques may be used in the case of poor fit, for example, negative-binomial regression. A secondary analysis to explore the possibility of intervention effect modification by hospital length of stay (e.g., longer stay may result in more deprescribing) will be implemented by considering the interaction of hospital length of stay with intervention.

**Hypothesis 1c:** The effect of intervention on the anticholinergic and sedative drug burden index scores at hospital discharge, SNF discharge, and 90-days following SNF discharge will be assessed using linear mixed effects

regression, adjusting for measurement time point, its interaction with intervention and using random effects, testing and summary methods as described for Hypotheses 1a, 1b and 1d. Model fit will be assessed using residual diagnostics and graphical methods. Due to the constrained nature of the DBI values, a ‘beta’ regression method may be required, which is suitable for scores that often occur at a boundary.

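### Four or five unranked primary medication outcomes are each tested with no stated alpha, order or success rule; if any one may be claimed, the chance of a false primary claim is about 9–19% (four) or 10–23% (five)

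*Combined protocol and SAP*

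**What the plan says.** All references are to the combined protocol and SAP.

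- **Study Design** lists "Primary Outcomes are change in total number (and/or dose) of medications including potentially inappropriate medications", followed by "number of medications associated with geriatric syndromes, and medications that contribute to anticholinergic and sedative drug burden". The list is not ranked. The same section makes geriatric syndromes, adherence and self-rated health secondary.
- **Précis, Overview and Objectives** describes the trial as powered for all four medication measures and gives each its own hypothesis (1a to 1d). For example, 1b reads "DROP will result in a significant reduction in the number of potentially inappropriate medications (PIMs) at hospital discharge" and goes on to SNF discharge and 90 days. It also says "Our Specific Aims reflect the primary outcomes that are the focus of the analyses".
- **Description of Assessments, Primary Outcomes – Medications** says of the DBI: "This score is calculated separately for anticholinergic and sedative medications".
- **Statistical Considerations, Outcomes** specifies for the count outcomes: "The overall intervention effect will be evaluated using a Wald-type multiple degree-of-freedom test against the null hypothesis of no effect at any time point". The DBI has a linear mixed model with "random effects, testing and summary methods as described for Hypotheses 1a, 1b and 1d". Each time point is summarized by a 95% interval.
- **Interim Analysis and Stopping Rules** excludes interim looks at efficacy.

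The statistical sections, from sample size to repeated measures, give no alpha, testing order, multiplicity adjustment or lead outcome. They do not say whether success needs one outcome, a particular outcome or all of them.

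**The concern.** Several outcomes carry the word primary, and each is tested for significance on its own. Without a decision rule, a report could present whichever outcome reached significance as the trial's primary result. The error rate of that claim would not be the error rate of a single test.

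A mixed result is also plausible. The protocol says the DBI will register dose reductions in cases where the number of drugs stays the same. If a DBI score fell and the count did not, two readers could reach opposite conclusions and both cite the plan. This sits badly with the plan's own reason for refusing early efficacy stopping, which is that changing practice needs firm evidence.

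**Working it through.** **The plan's own figure.** No familywise error rate is stated, so there is none to reproduce. The nearest figure is power above 93% with 260 Veterans (Sample Size and Randomization). It comes without an effect size, standard deviation, alpha or named outcome, so it cannot be checked. In a simple comparison of two means with 130 per arm at two-sided 0.05, 93% power needs a standardized effect of about 0.43.

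**Inputs**

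- Number of tests, k: 4 if the DBI counts once, 5 if its two scores are tested separately.
- Level per test: two-sided 0.05. This is an assumption, inferred from the 95% intervals.
- True state: no effect on any outcome.
- Claim rule: any one significant result counts.
- Correlation between outcomes, ρ: not given. The range 0 to 0.9 is assumed. Positive correlation is expected, because the outcomes are drawn from the same medication lists.
- One analysis set is counted, although both intent-to-treat and per-protocol analyses are planned.
- Time points: one multiple-degree-of-freedom test per outcome covers hospital discharge, SNF discharge and 90 days, so they do not multiply k.

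**Independent tests.** The chance of at least one false positive is 1 − (1 − 0.05)^k.

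- k = 4: 1 − 0.95^4 = 1 − 0.8145 = 18.5%
- k = 5: 1 − 0.95^5 = 1 − 0.7738 = 22.6%

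**Equally correlated tests.** With c = 1.96, the chance is

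1 − ∫ φ(u) [Φ((c − √ρ·u)/√(1−ρ)) − Φ((−c − √ρ·u)/√(1−ρ))]^k du,

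evaluated numerically. The planned 3-df Wald tests were also simulated (300,000 replicates, same correlation between outcomes at each time point).

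| ρ | k = 4, single statistic | k = 5, single statistic | k = 4, 3-df Wald | k = 5, 3-df Wald |
|---|---|---|---|---|
| 0 | 18.5% | 22.6% | 18.6% | 22.6% |
| 0.5 | 15.6% | 18.3% | 16.0% | 18.9% |
| 0.7 | 13.0% | 14.8% | 13.4% | 15.4% |
| 0.9 | 9.4% | 10.2% | 9.7% | 10.5% |

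The form of the test hardly matters. The correlation does, but even at 0.9 the figure is about twice 5%.

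**Cost of splitting alpha.** Bonferroni levels are 0.05/4 = 0.0125 and 0.05/5 = 0.01. If the stated 93% came from an effect of about 0.43 standard deviations at 0.05, power per outcome would be about 83% and 81% at those levels.

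**The case against.** The strongest reply is that the inflation is read into silence. The plan nowhere says that one significant outcome makes the trial a success. If all outcomes had to succeed, there would be no inflation. If 1a to 1d are four separate claims, each has its own error rate. This stands in part: the percentages hold only under the any-one-counts reading. It does not remove the gap, because the plan adopts none of these readings.

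The null assumption is also pessimistic. In the pilot, an average of 12.6 medications were deprescribed in the intervention group against 6.5 in controls (P < .001). If the effect on the count is real, three or four nulls remain, and the independent-test figures become 1 − 0.95^3 = 14.3% and 1 − 0.95^4 = 18.5%. The upper end for five tests also needs independence, which is implausible for measures taken from the same lists. Both points stand, and are why a range is given.

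The plan deserves credit for the joint test over time and for having no efficacy looks.

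Three stronger readings are tempting:

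- A reader might infer that all Aim 2 outcomes are primary, from the Précis sentence on the Specific Aims. Study Design and the Description of Assessments call them secondary, so this is a wording conflict rather than a larger primary family.
- A reader might count adherence (ARMS) as a sixth primary test, giving 1 − 0.95^6 = 26.5%, because the Schedule of Assessments places it under the primary heading. The same two sections contradict that.
- A reader might count every time-point interval as a test. Twelve or fifteen tests would give about 21–41% under assumed correlations of 0.5–0.9 over time and 0.5–0.7 between outcomes. The plan uses those intervals as summaries and bases the overall effect on the joint test.

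**Conclusion.** The concern holds in a limited form. The plan has four unranked primary medication outcomes, five with separate DBI scores, and no alpha, order, adjustment or success rule. The chance of at least one false primary claim is about 9–19% for four and 10–23% for five. This rests on two-sided 0.05 per test, every null true, any single significant result being claimable, and correlations from 0.9 down to 0. None of these is stated in the documents.

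A reader might infer that the plan endorses claiming success on any one outcome, or that its error rate is simply 18.5% or 22.6%. The documents support neither: the first is only left open, and the second needs independent outcomes. The effect estimates and intervals are not invalidated. What is undefined is the confirmatory conclusion.

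**What to change.** State a familywise two-sided alpha of 5%. Before outcome data by arm are seen, fix this sequence, using the overall Wald test at each step:

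1. Total number of medications, the target of Specific Aim 1.
2. PIMs (1b).
3. Anticholinergic DBI (1c).
4. Sedative DBI (1c, as its own step).
5. Syndrome-associated medications (1d).

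Stop formal claims at the first non-significant result and report the rest as estimates with intervals. The order follows the hypothesis lettering in the Précis. Study Design lists syndrome-associated medications before drug burden, so the choice should be stated. Holm across the outcomes is acceptable, but its first step uses 0.0125 or 0.01.

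Two wording changes are also needed:

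- Say that the lead outcome is the medication count and that dose reductions are assessed through the DBI. Study Design and Hypothesis 1a now mix number and dose.
- Align the Précis sentence on the Specific Aims and the ARMS row of the Schedule of Assessments with Study Design, which makes Aim 2 outcomes secondary.

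The change is to wording only, and the first test keeps the full 5%. The price is that later outcomes lose confirmatory status if an earlier one fails. Dose reductions in drugs outside the DBI would be described but not formally tested.

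Timing matters. Study Design ends follow-up in March 2023, and a sequence chosen after results are known protects nothing. If results have been seen, report all the outcomes together and state openly that multiplicity was not controlled.
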